6.3.3 Criteria and Procedures for Treatment/Investigation Withdrawal or Discontinuation

There are no pre-defined criteria for temporary or permanent treatment discontinuation apart from those listed below.

The patient may voluntarily withdraw from the clinical investigation at any time without penalty and for any reason without prejudice to his/her future medical care (Declaration of Helsinki).

The patient must be withdrawn from the clinical investigation if, in the opinion of the investigator, there is any situation or condition which puts the patient at significant risk, especially in case of:

- Any safety reason(s)/AEs necessitating discontinuation from the investigation,
- Any abnormality with IMD,
- Lack of performance: if the patient or the investigator does not feel that the IMD has sufficiently controlled the pathology/has adequately relieved his/her symptoms,
- Patient compliance,
- Patient's request,
- Any exceptional circumstance (e.g., COVID-19 pandemic),
- Other reasons.

If a patient has received a prohibited medication, the investigator may withdraw the patient from the clinical investigation if it can interfere with the patient safety or data integrity. If no risk is identified, the patient may continue the clinical investigation. This will be recorded as a protocol deviation and managed accordingly. The Sponsor may also make the decision to withdraw a patient if a risk is suspected.

If a patient prematurely stops the IMD or should/wants to prematurely withdraw from the clinical investigation for any reason, the investigator (or delegated assessor) must make every effort to perform all the evaluations described for the Final Visit (Visit#4) as soon as possible.

The investigator (or delegated assessor if physician) will prescribe the best appropriate treatment to the patient.

Additionally, Sponsor can terminate the clinical investigation per reasons discussed in Section 16.2.

In all cases, the reason(s) for withdrawal, must be recorded on the patient files (source documentation) and the primary reason, must be recorded on the e-CRF.

The patient discontinued for AE(s) will be followed-up after discontinuation until the event is resolved or considered medically stable by the investigator.

If a patient is lost-to-follow-up, the investigator must do his/her best to contact the patient initially by phone, then by letter, and finally by certified mail. If no response is obtained from the patient, the investigator is encouraged to contact one of the patient's relatives or his/her general practitioner. The evidence of these contacts must be recorded in the patient files.

Screen failures are defined as patient who consent to participate in the clinical investigation and undergo Visit#1 but are not subsequently randomised in the clinical investigation.

If a patient is screen-failed, all reasons of screen-failure must be documented in the Source document. The screen-failed patient may be rescreened one time.

The Procedures for the replacement of patients is described in section **6.1.7**.

Adaptive follow-up in the case of an **exceptional circumstance (e.g. COVID-19 pandemic)** is described in section **0.0**

6.3.4 Point of Enrolment

The point of enrolment corresponds to the time at which a patient signs and dates his/her consent form. Patients are to be enrolled at about 4 investigational sites in EU.

6.3.5 Point of Randomisation

The point of randomisation corresponds to the time at which a patient is assigned with a randomisation number. This randomisation number will be allocated when all Inclusion / Exclusion criteria are verified.

6.3.6 Total Expected Duration of the Clinical Investigation

This investigation is planned to start in August 2024 and to be completed in April 2025.

6.3.7 Expected Duration of each Patient's Participation

The treatment period for each patient is 36 ± 3 days for a total maximum investigation duration of 49 days (maximum days comprising the run-in, treatment period).

[figure not shown]
6.3.8 Number of Patients Required to be Randomised in the Clinical Investigation

It is planned to randomise 74 patients in order to have 68 evaluable patients (34 per group) for the FAS analysis.

Evaluable patients will be defined as randomised patients having received at least one dose of IMD and with at least one performance endpoint post-randomisation visit.

6.3.9 Estimated Time Needed to Select this Number (i.e. enrolment period)

The enrolment period is estimated at about 6 months.

6.3.11 Information on Vulnerable, Pregnant, and Breastfeeding Population

This clinical investigation will not be conducted in vulnerable populations as children, pregnant or breastfeeding women. A urine pregnancy testing will be performed at Visit#1 and Visit#4 (See Section **15**).

6.4 PROCEDURES

Some procedures must be performed by the same masked investigator or the same authorized assessor/delegate throughout the clinical investigation (Far BCVA, Slit Lamp Examination, Schirmer test, tolerance/performance assessment by investigator).

6.4.1 Description of all the Clinical-Investigation-Related Procedures that Patients Undergo during the Clinical Investigation.

6.4.1.1 Demographics and Screening Characteristics

The following characteristics will be collected:

- Age (in years),
- Sex,
- Previous and concomitant ocular and non-ocular medications,
- Result of the urinary pregnancy test (only for women of childbearing potential),
- History of the investigated disease,
- Ocular medical and surgical history with relevant diagnosis other than the investigated disease,
- Systemic medical and surgical history with relevant diagnosis

6.4.1.2 Performance Measures

6.4.1.2.1 Ocular Surface Disease Index (OSDI) Questionnaire

The OSDI questionnaire (Schiffman et al., 2000; Miller et al., 2010) must be completed by the patient at the beginning of a visit before medical history information is collected or any investigation assessments are performed. The total OSDI score range on a scale from 0 to 100

6.4.1.2.3 *Ocular discomfort (VAS)*

Ocular discomfort (global evaluation for both eyes) will be assessed by the patient at D1, D15 and D36 visits according to the following:

“Please mark a vertical line (not a cross) on the horizontal line, indicating your level of ocular discomfort due to ocular dryness within the last 48 hours”. VAS will be a 100 mm line: 0 mm = No discomfort, 100 mm = Maximal discomfort.

6.4.1.2.4 *Dry eye related ocular symptoms throughout the day within the last 48 hours*

Patient will be asked: “How do you judge the severity of the following ocular symptoms throughout the day within the last 48 hours, excluding the symptoms you felt immediately after instillation?”

The severity of the following ocular symptoms will be assessed: burning/irritation, stinging/eye pain, light sensitivity, itching/pruritus, eye dryness feeling, tearing, foreign body sensation as follows:

0 = Absent

1 = Mild, present but not disturbing

2 = Moderate, disturbing, but not limiting with daily activities

3 = Severe, very distressing and interfering with daily activities

The ocular symptoms will be assessed in global for both eyes at D1, D15 and D36 visits. The value at D1 will be the baseline value.

6.4.1.2.5 *Slit lamp examination*

- Conjunctival hyperaemia

The level of severity of conjunctival hyperaemia will be scored [REDACTED] in each eye and at D1, D15 and D36 visits (see Section 19.4).

- Tear Break-Up Time (TBUT)

The tear film stability will be measured 3 times after the instillation of fluorescein. TBUT will be rapidly assessed and expressed in seconds. The sum of the 3 measures will also be expressed in seconds. TBUT will be measured in each eye and at D1, D15 and D36 visits.

- Ocular surface staining ([REDACTED] Oxford scale)

The total ocular staining grade using [REDACTED] Oxford 0-15 grading scheme will be assessed at D1, D15 and D36 visits by staining in corneal area by fluorescein and conjunctival areas (temporal and nasal) by fluorescein with a yellow filter.

Cornea and conjunctiva staining is represented by punctate dots on a series of panels (A-E). Staining ranges from 0-5 for each zone and from 0-15 for the total exposed inter-palpebral

conjunctiva and cornea. The dots are ordered on the log scale ([REDACTED] Oxford scale) (see Section 19.5).

The score for each area will be recorded for each eye. The global score (sum of score reported for each area: corneal + conjunctival) will be used for statistical analysis. The statistical analysis will be performed following original oxford scale [REDACTED]

TBUT and ocular surface staining will be assessed after micro instillation of fluorescein. Some drops of fluorescein are put in a petri dish and a small amount of fluorescein is collected with an inoculation loop and then applied to the upper bulbar conjunctiva. This process will be detailed in a specific guide provided to investigation sites.

A slit lamp examination will also be performed at Visit #1 (Screening visit) for evaluation of the prohibited ophthalmic conditions in order to verify the ocular eligibility.

6.4.1.2.6 *Schirmer Test*

The Schirmer test will be performed without anaesthesia (Test I). The test should be done **without touching directly the strip with the finger** to avoid contamination of skin lipids.

The strip should be placed in the temporal part to avoid any contact with the cornea. The patient should keep the eyes closed. Values should be measured just at the end of the 5 minutes.

The Schirmer test will be measured in mm/5 min in each eye and at D1, D15 and D36 visits.

6.4.1.2.7 *Performance Assessment by the investigator*

The investigator must answer to the following question at the end of the patient examination at D15 and D36:

“Do you consider the IMD performance as:

- Very satisfactory
- Satisfactory
- Not very satisfactory
- Unsatisfactory”

6.4.1.2.8 *Global performance by patient*

The global performance is assessed by the patient using a vocal NRS scale. The investigator must ask the following question in local language:

“In a scale from 0 to 10, where 0 is COMPLETELY UNSATISFIED and 10 is COMPLETELY SATISFIED, indicate the number which corresponds the best to your overall satisfaction with the efficacy of the study product in treating your dry eye” (see Section 19.7).

The patient must answer the question verbally.

6.4.1.2.9 *Tear level of inflammatory cytokines (IL-6 and IL-8)*

A tear sampling of at least 5 µL will be performed at D1, D15 and D36 in the study eye using a method which is defined in a specific guide. The sample will be analysed by central laboratory in order to assess the level of inflammatory cytokines in tears. The Tear sampling will be done after answer to patients’ questionnaires and before ocular examinations.

To prevent the tear sampling from interfering with other ocular assessments, it will be required to wait at least 15 minutes after the sampling is performed to continue with the next ocular assessment.

6.4.1.3 *Safety measures*

6.4.1.3.1 *Adverse Events*

Ocular and systemic AEs will be collected by the investigator (or authorised assessor/delegate) at each visit. In case of appearance of a new clinically significant sign or symptom, it should be reported as an AE. In case of clinically significant worsening of a pre-existing sign or symptom, it should be reported as an AE.

The handling of AEs is detailed in Section 0.

6.4.1.3.2 *Incidents*

Incidents will be collected by the unmasked investigator (or authorised assessor/delegate) at D1, D15 and D36 visits.

6.4.1.3.3 *Ocular Symptoms immediately after drop instillation*

The severity of ocular symptoms immediately after drop instillation will be assessed by the patient.

“Since the last visit, have you felt any unusual ocular sensation immediately after drop instillation(s)?

The following symptoms will be evaluated:

- Burning/Irritation
- Stinging/Eye Pain
- Itching/pruritus
- Eye dryness feeling
- Foreign body sensation
-

Severity will be assessed based on a 4-point scale:

- 0 = Absent,
- 1 = Mild - Present but not disturbing,
- 2 = Moderate - Disturbing
- 3 = Severe - Very disturbing.

The translation of these terms will be provided to the site.

6.4.1.3.4 *Visual Acuity*

Far BCVA will be assessed in each eye at each visit using the same chart (for example a Snellen chart) throughout the clinical investigation. It can be expressed using units as /10, decimal notation, MAR, logMAR, ETDRS or Snellen notation. It will be analysed after conversion in LogMar. (see Section 19.6).

6.4.1.3.5 *Ocular Tolerance Assessment by the investigator*

The investigator must answer to the following question in local language:

“How do you consider the IMD ocular tolerance?

- Very satisfactory
- Satisfactory
- Not very satisfactory
- Unsatisfactory”

6.4.1.3.6 *Ocular Tolerance Assessment by the Patient*

The investigator must ask the patient the following question in local language:

“How do you consider the study treatment ocular tolerance?

- Very satisfactory
- Satisfactory
- Not very satisfactory
- Unsatisfactory”

6.4.1.3.7 *Treatment Compliance Evaluation*

Patient will return all investigational products (IMDs and Hydrabak®), whether used or unused.

For Hydrabak® and IMD (T2769 or Hylo-Forte®), the patient will also have to report information about his/her compliance on a paper patient diary during the run-in and the treatment period. Each day the patient will enter the date and number of instillations* per day. Moreover, it will be asked to add the date and hour of last instillation before the beginning of each visit.

In addition, compliance will be assessed by questioning the patient during the visit (e.g. if there was any treatment interruption or missed instillation), by checking on paper patient diary and by cross-checking with IMD accountability information provided by unmasked collaborator.

* one instillation = 1 drop in each eye

6.4.1.4 *Prior and Concomitant Therapy*

At screening visit, patient will be asked what treatment he/she has taken within the last 3 months; this will be recorded on the patient medical record and on the e-CRF documenting product details, dose and treatment duration.

Concomitant treatment means any medications or non-medicinal therapies given concurrently with the IMD. Any other local or systemic treatment necessary for the patient's welfare has also to be recorded on the patient medical record and on the e-CRF documenting product details, dose and treatment duration. In case of premature discontinuation, the new treatment for dry eye with the start date and dosing must also be collected.

6.4.1.5 *Permitted Treatments*

Auxiliary products are permitted (see Section 0). Systemic medication not listed in **Table 2** are permitted **ONLY** if there has been no modification of the dosage in the month preceding the inclusion visit and if no modification is planned throughout the duration of the study.

6.4.1.6 *Prohibited Prior and Concomitant Medications or Treatments*

6.4.1.6.1 *Rescue Medications (RMs)*

NA.

6.4.1.6.2 *Prohibited Treatments other than Rescue Medications (RMs)*

Prohibited treatments as well as prohibited modifications during the clinical investigation are presented in the summary in the exclusion criteria and in **Table 2**.

6.4.2 **Description of those Activities Performed by Sponsor Representatives (excluding monitoring)**

Laboratoires THÉA through CROs is responsible for selecting the investigator(s). Each investigator should be qualified by training and experience and should have adequate resources to properly conduct the clinical investigation.

Laboratoires THÉA /representatives of Laboratoires THÉA will remind the investigator upon his/her responsibilities and procedures for ensuring adequate and correct documentation.

Laboratoires THÉA will inform the investigator, directly or through CRO in charge of monitoring, prior to the commencement of the clinical investigation of all relevant chemical, toxicological and clinical information required for the proper planning and conduct of the clinical investigation and will update this as often as may be necessary during the course of the clinical investigation. However, this obligation shall not require Laboratoires THÉA to provide information which is already available in published material or of which the investigator could reasonably be expected to have knowledge in view of his/her professional training.

Laboratoires THÉA or CROs will nominate a suitably trained person or persons to monitor the clinical investigation and to liaise with the investigator.

Laboratoires THÉA/representatives of Laboratoires THÉA, will also be responsible for complying with the local regulations applicable to clinical investigation.

6.4.3 **Any Known or Foreseeable Factors that may Compromise the Outcome of the Clinical Investigation or the Interpretation of Results**

The population will be selected according to the inclusion and exclusion criteria to have a homogenous population.

A run-in period with Hydrabak® is scheduled to have patient with the same treatment at the baseline visit.

6.4.4 **Methods for Addressing these Factors in the Clinical Investigation**

To not compromise the outcome of the clinical investigation, the patient will be randomly assigned to 1 of the 2 treatment groups during the randomisation visit.

6.4.5 **Description of the Follow-Up Period**

NA

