6 DESIGN OF THE CLINICAL INVESTIGATION

6.1 GENERAL

6.1.1 Justification of the Investigation Design

Methodology: a 5-week, international, multicentre, randomised, investigator-masked, 2 parallel groups (T2769 versus Hylo-Forte®) investigation.

- Multicentre

The investigation will be performed in different sites in EU.

A multicentre (and multi-investigator) design will provide the possibility of recruiting the patients from a wider population than a single-centre design and of using the device in a broader range of clinical settings, thus presenting an experimental situation that is more typical of future use. In this case, the involvement of a number of investigators also gives the potential for a wider range of clinical judgments concerning the value of the therapeutic intervention. In addition, it is also a practical means of accruing sufficient patients to satisfy the investigation objective.

- Randomised

At the randomisation visit on Day 1, a patient fulfilling all eligible criteria will be randomly assigned to 1 of the 2 treatment groups (T2769 or Hylo-Forte®). Randomisation ensures the investigator remains masked to product assignment for DES treatment. It is generally considered the most reliable method for evaluating the effects of interventions.

- Choice of run-in period

Patients meeting the screening criteria will undergo a 7-10-days run-in period. During this period, all patients will substitute their current dry eye treatment with Hydrabak®, ophthalmic solution containing NaCl 0.9%. Patients will instill 1 drop in each eye, from 3 to 6 times daily.

[Redacted content block] (Baudouin et al. 2017; Chiambretta et al. 2017; Labetoulle et al. 2018; Holland et al. 2019).

- Investigator-masked

A double-masked investigation design is not possible due to different commercial packaging between T2769 – Hylo-Forte®.

However, the identity of the IMD given to each patient will not be known for the masked investigator who is independently in charge of the ophthalmic examination.

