By the masked investigator or authorised delegate (the same as the screening visit) (according to local requirements, the investigator may delegate tasks to collaborator).

- Questioning about previous and concomitant ocular and non-ocular treatments
- OSDI Questionnaire
- DEAL questionnaire
- Ocular discomfort (VAS)
- Questioning about ocular symptoms immediately after drop instillation,
- Questioning about dry eye related ocular symptoms within the last 48 hours
- Assessment of global performance by the patient
- Assessment of the ocular tolerance by the patient
- Measurement of Far BCVA*
- Tear Sampling for IL6 and IL8 concentration assessment**
- Slit lamp examination* for measuring:
 - Measurement of conjunctival hyperaemia* [REDACTED]
 - [REDACTED] Oxford 0-15 grading scheme* (corneal and conjunctival staining by fluorescein with yellow filter)
 - TBUT*
- Schirmer test* (without anaesthesia)
- AE reporting
- Assessment of the ocular tolerance by the investigator
- Assessment of the performance by the investigator
- IMD dispensation
- Questioning about IMD compliance
- Check of the patient diary completion with the patient

*Ophthalmological examinations and assessments MUST be performed by the SAME masked investigator for all the visits and using the same slit lamp.

**It's necessary to wait at least 15 minutes after tear sampling to perform the next ophthalmic assessment.

By the unmasked collaborator:

- Recording the number of returned used and unused IMD in source document (the accountability is expected for the quantity of bottles) and transfer this information to masked investigator for compliance assessment.
- Incidents reporting

The next visit must be scheduled 36 days after Visit #2 (± 3 days) at the same hour (± 2 hours).

Site staff must remind the patients:

- how to complete the patient diary,
- to not report any information that could lead to unblinding in the diary,
- to not report any information that could lead to unblinding to the masked investigator,
- to bring the patient diary back at Visit #4.
- how to instil IMD and to respect the posology of 1 drop in each eye, from 3 to 6 times daily,
- that no IMD must be instilled for at least 2 hours before Visit#4.

Visit#4: Day 36 (± 3 days)

Visit#4 will consist of the following procedures and examinations by the investigator or authorised delegate who will perform the ophthalmologic examination during all the visits and according to the following order in each eye.

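### At Visits 3 and 4 the default procedure has the masked examiner hear a product-aware patient's symptom, satisfaction and tolerance answers before grading the primary endpoint, which leaves a route for evaluator bias

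*Protocol*

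**What the plan says.** **Patient masking.** Protocol 6.1.1: "A double-masked investigation design is not possible due to different commercial packaging". The patient handles the bottle and can recognise the product.

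**Who runs the visit, and in what order.** Protocol 6.1.5.2 has Visits 3 and 4 conducted "by the investigator or authorised delegate who will perform the ophthalmologic examination during all the visits and according to the following order". The list under the masked investigator or delegate includes "Questioning about ocular symptoms immediately after drop instillation", then symptoms over the last 48 hours, then "Assessment of global performance by the patient", then the patient's tolerance rating. BCVA, tear sampling and the slit lamp with Oxford grading follow.

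**Who asks.**
- Satisfaction (6.4.1.2.8): "The global performance is assessed by the patient using a vocal NRS scale. The investigator must ask the following question in local language". The next instruction is "The patient must answer the question verbally".
- Patient tolerance (6.4.1.3.6): "The investigator must ask the patient the following question in local language".
- The two symptom items (6.4.1.2.4 and 6.4.1.3.3) name no interviewer, but they sit on the same task list.

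**Who grades.** A note in 6.1.5.2 requires the same masked investigator to perform the ophthalmological examinations at every visit.

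**What the protocol says about bias.** Section 6.1.2.3 names evaluator bias as a serious risk and gives masking as the protection.

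**The concern.** Oxford staining is graded by visual judgement. A grader who has just elicited how satisfied the patient is, and how well the drop was tolerated, may lean towards a grade that agrees. The patient gives those answers knowing the product, so the opinion can differ between arms for reasons unrelated to the ocular surface. An investigator-masked design exists to keep such influence away from the grader.

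The protocol closes neighbouring channels. The masked investigator does not receive returned bottles, and incident reports go to an unmasked collaborator because they might unblind. The investigator's own performance and tolerance ratings are listed after the examination. The patient's ratings are listed before it.

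At stake is the masked reading of the primary endpoint. TBUT, hyperaemia and the Schirmer test are exposed in the same way, because the same examiner measures them later in the visit.

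**Working it through.** **1. Tracing the default path (Protocol 6.1.5.2, Visits 3 and 4)**

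| Step | Under the masked investigator or delegate | Also asked at D1? |
|---|---|---|
| Post-instillation symptoms | yes | no |
| 48-hour symptoms | yes | yes |
| Satisfaction, 0-10, spoken | yes; investigator must ask | no |
| Patient tolerance | yes; investigator must ask | no |
| BCVA, tear sampling, wait of at least 15 minutes | yes | BCVA, sampling and wait: yes |
| Slit lamp with Oxford grading | same masked investigator throughout | yes |

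Two things follow. First, no visible text requires the interviewer to differ from the grader, or the answers to be withheld until grading is done. Second, three of the four items are absent at D1, so any influence from them enters only the D15 and D36 grades and does not cancel in the change from baseline. The 48-hour question is asked at D1 too, but before any study product has been used.

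**2. Inputs for an illustration of size**
- 34 evaluable per group and 74 randomised (Protocol 6.3.8).
- Margin +2 points and a two-sided 95% CI, so one-sided 0.025 (Protocol 7.2.1).
- SD, power and dropout rate do not appear in the public text, so the sample size cannot be strictly reproduced. It is consistent with a dropout of 1 - 68/74 = 8.1%. At 34 per group the implied SD is 2 × √(34/2) / (1.960 + z): 8.246/2.802 = 2.94 at 80% power and 8.246/3.242 = 2.54 at 90% power.
- SD 2.5 is therefore assumed, with a range of 2.0 to 2.9.
- The shift s, the differential grading bias between arms, is assumed. Nothing in the documents gives it.

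**3. Formula.** SE = SD × √(2/34). One-sided error at a true difference of +2 = P[noncentral t(66 df, s/SE) > 1.997].

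For SD 2.5, SE = 2.5 × 0.2425 = 0.606. With s = 0.25 the noncentrality is 0.25/0.606 = 0.412.

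| Assumed SD | SE | s = 0 | s = 0.25 | s = 0.5 |
|---|---|---|---|---|
| 2.0 | 0.485 | 2.5% | 7.3% | 17.3% |
| 2.5 | 0.606 | 2.5% | 6.0% | 12.6% |
| 2.9 | 0.703 | 2.5% | 5.4% | 10.4% |

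A shift against T2769 costs power instead. With no true difference and SD 2.5, power falls from 90% to 68% when s = 0.5.

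This is a two-sample approximation to the planned MMRM. It shows how sensitive the test is to any differential grading bias of that size. It does not estimate the bias that this procedure causes.

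**The case against.** - **Delegation is allowed.** True. Protocol 6.4 lists the tasks that must stay with one assessor, and the patient interviews are not among them. A site may already separate interviewer from grader. But separation is optional, so with about 4 sites the exposure depends on local practice.
- **Patients are trained not to disclose.** True, and this protects against naming or describing the product. It cannot cover ratings that the investigator is instructed to elicit.
- **Time passes before grading.** BCVA, tear sampling and at least 15 minutes intervene. The answers are heard earlier in the same visit, not immediately before grading. The wait is there so that sampling does not disturb the next measurement; it does not remove what was heard.
- **Only a differential effect matters.** This stands. If satisfaction is similar in the two arms, much of any halo effect cancels in the between-group difference. The documents give no reason to expect a particular direction.
- **Unseen text may help.** Redacted sections and the site guides could contain a safeguard.

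A reader might infer more than the text supports. One such inference is that the drop-sensation answers unmask the grader. No visible text says that the two products feel different, the listed symptoms are generic to eye drops, and a score or rating names no bottle. Another is that Oxford grading is the trial's only masked assessment. It is not, since the other signs share the same masked examiner. A third is that the error rate is in fact inflated. The percentages rest on assumed shifts and an assumed SD, and they apply only at a true difference of exactly +2.

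**Conclusion.** The concern holds as a gap in the procedures that protect masked grading. By default, and subject to optional delegation, the grader of the primary endpoint first elicits the opinion of a patient who knows the product. That opens a route for evaluator bias into Oxford staining and the other masked signs. The documents neither contradict themselves here nor contain an analysis error, and nothing shows that bias has occurred.

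The size and direction are unknown. The illustrative rise from 2.5% to about 6% (5.4% to 7.3% for SD 2.9 to 2.0) requires a differential shift of 0.25 point favouring T2769, which is one eighth of the margin. The change is worth making because the remedy is cheap and the endpoint is the primary one.

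**What to change.** In Protocol 6.1.5.2 (Visits 3 and 4), 6.4.1.2.4, 6.4.1.2.8, 6.4.1.3.3 and 6.4.1.3.6:

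1. Have the patient complete the post-instillation symptoms, 48-hour symptoms, satisfaction score and tolerance rating on paper, in their present place before the examination. Protocol 6.5.1 already has OSDI, DEAL and the VAS collected on paper.
2. State that the masked examiner does not see these answers until the Oxford, TBUT, hyperaemia and Schirmer results for that visit are entered. Paper without this rule would not close the route.
3. Remove the instructions that the investigator asks the satisfaction and tolerance questions, and that the satisfaction answer is spoken.

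For consistency, the 48-hour item should be on paper at D1 as well.

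The questions should not be moved to the unmasked collaborator. That would put an unmasked interviewer between the patient and subjective ratings. It may also need extra staff time where the hospital pharmacy does the bottle counts.

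**Cost.** A short amendment, which Protocol section 9 requires to be approved before use, and a site training note. The satisfaction scale changes from spoken to written. If enrolment has begun, record the date of the change so that answers collected in the two modes can be told apart.
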